**Figure 3 Diagram of Study Design**

\* Patients who, for any reason, withdraw from the study treatment will be highly encouraged to continue attending all their remaining study visits to collect the most complete efficacy and safety data.

#### 4.2 Justification for Study Design

This is a randomized, parallel group, double-masked, placebo-controlled, multicenter study, efficacy, safety and tolerability phase 3 study. Full details on study design are presented in Section 4.1.

Clobetasol propionate is marketed in the US for short-term topical use since 1985 (Temovate® Cream) and under many different proprietary names (Clobesate®, Cormax®, Embeline®, Olux®, Clobex®, etc...) over the years, showing a positive benefit-risk profile with a good long-term safety profile. There is extensive non-clinical documentation on chemical and pharmaceutical properties, pharmacology, PK, and toxicology of clobetasol propionate covering various routes of administration, including ocular administration.

Additionally, the Sponsor has conducted its own non-clinical studies to assess the Clobetasol propionate ophthalmic nanoemulsion 0.05% efficacy and safety profile (Section 2.1.3) and considers this non-clinical data sufficient to support a human phase 3 study.

The study is double-masked, and placebo controlled to ensure unbiased data collection and to account for the placebo effect.

### 4.3 Study Conduct

#### 4.3.1 Schedule of Observations

A schedule of observations and assessments to be performed during the study is provided in Table 1.

**Table 1 Schedule of Observations**

Visit number	Visit -1 Screening	Cataract Surgery	Visit 1 Baseline	Visit 2	Visit 3	Visit 4	Visit 5	Early termination
Study time-point	Day -7 (± 3 days)	Day -1	Day 1	Day 3 (+ 1 day)	Day 8 (± 1 day)	Day 15 (± 2 days)	Day 29 (± 2 days)	
Eligibility criteria	X		X					
Dated and signed Informed consent for study participation 	X							
Demographic data	X							
Relevant medical history 	X		X					
Prior medications 	X		X					
Urine pregnancy test	X		X					
Eye pain (VAS) 	X		X	X	X	X	X	X
Eye discomfort 	X		X	X	X	X	X	X
Photophobia (VAS) 	X		X	X	X	X	X	X
Vital signs examination 			X	X	X	X	X	X
Physical and eye examination	X							X
Slit-lamp examination	X		X	X	X	X	X	X
Intraocular pressure	X		X	X	X	X	X	X
Best-corrected visual acuity Snellen	X		X		X	X	X	X
Indirect ophthalmoscopy	X		X			X	X	X
Randomization			X					
Dispensation of IMP			X					
Administration of first IMP dose			X					
Distribution of patient diary			X					
Review of patient diary				X	X	X		X 
Return of patient diary						X		X 

Return of remaining IMP						X		X 
Adverse events 	X		X	X	X	X	X	X
Concomitant medications			X	X	X	X	X	X
End of study							X	X

Abbreviations: IMP, investigational medicinal product; VAS, visual analog scale.

All ocular assessments must be performed in both eyes.

1. Informed consent must be signed and dated prior to any study-related procedure and before any data is recorded in the case report form
2. Relevant medical history will include any previously diagnosed ophthalmic abnormalities and ocular surgeries (including laser procedures). Relevant medical history at Visit 1 (Day 1) will cover the time from the Visit -1 (Screening).
3. Medications taken 2 months prior to Visit -1 (prior 36 months for ocular implants and/or intravitreal injections)
4. VAS scales and discomfort should be assessed prior to any physical evaluation
5. Vital signs assessments to be completed 15 min before any ocular assessment. Additionally, baseline Vital signs on Visit 1 to be completed at least  $30 \pm 10$  min before IMP administration.
6. If occurred within the 14 days planned for the treatment period.
7. Expected changes or the presence of inflammation or pain resulting from routine cataract surgery will not be captured as adverse events.

#### 4.3.2 *Observations by Visit*

The study assessments described in the sections below are presented in detail in Section 7.2 (Primary Efficacy Assessments), Section 7.5.1 (Demographic and Baseline Data) and Section 8 (Assessments of Safety). Recording and reporting of AEs are described in detail in Section 8.3.

The day of the cataract surgery will be considered Day -1 of the study, whereas the day of the randomization and the first administration of the IMP will be considered Day 1 of the study.

The order of the assessments/activities within a visit will be performed depending on the center/investigator's preference, with the exception of:

- Written informed consent at Visit -1 (Screening visit) should be obtained before any study specific procedure.
- Assessment of inclusion/exclusion criteria at Visit 1 (Baseline) before any other study assessment/activity.
- VAS scales should be assessed prior to any physical evaluation throughout the study.
- Vital signs should be obtained at least 15 min before any ocular assessment throughout the study. Additionally, at Visit 1 vital signs should be obtained at least  $30 \pm 10$  min before IMP administration. Vital signs should be obtained for a patient in the same manner throughout the study, for instance obtained from the same arm.
- Assessments/activities at Visit 1 that should be performed before the IMP administration.

The timing of all study events is shown in Table 1.

An attempt should be made to schedule patients at approximately the same time during the day at each study visit.

Detailed information on study assessments is provided in Sections 7 and 8.

---

**4.3.2.1 Visit -1 (Screening visit at Day -7 ± 3 days)**

This visit will be coincident (whenever possible) with the standard of care pre-surgery scheduled visit.

Before participating in the study, patients will be informed both verbally and in writing about the purpose of the study, its procedures and any risks or discomforts involved with participation.

A signed ICF must be obtained from each participant before any study-related procedure can take place. Only patients who fulfil all eligibility criteria (Section 5) will be enrolled in the study.

At Visit -1, the following activities and assessments will be performed (**NOTE:** All ocular assessments must be performed in both eyes):

- ICF signature
- Inclusion/exclusion criteria assessment
- Demographic data
- Relevant medical history
- Prior (2 months; 36 months for ocular implants and/or intravitreal injections) medications
- Urine pregnancy test – only for females of childbearing potential
- Eye pain (VAS) – to be assessed prior to any physical evaluation
- Eye discomfort – to be assessed prior to any physical evaluation
- Photophobia (VAS) – to be assessed prior to any physical evaluation
- Physical and eye examination
  - Slit-lamp examination
    - ✓ Anterior chamber cell
    - ✓ Anterior chamber flare
    - ✓ Chemosis
    - ✓ Bulbar conjunctival injection
    - ✓ Ciliary injection
    - ✓ Corneal edema
    - ✓ Keratic precipitates
  - IOP
  - BCVA measured by Snellen chart
  - Indirect ophthalmoscopy
  - Adverse events assessment

**4.3.2.2 Visit 1 (Baseline visit at Day 1, 24 h after the cataract surgery)**

At Visit 1, the following activities and assessments will be performed (**NOTE:** All ocular assessments must be performed in both eyes):

Prior to IMP administration:

- Inclusion/exclusion criteria assessment
- Relevant medical history
- Urine pregnancy test – only for females of childbearing potential
- Eye pain (VAS) – to be assessed prior to any physical evaluation
- Eye discomfort – to be assessed prior to any physical evaluation
- Photophobia (VAS) – to be assessed prior to any physical evaluation
- Vital signs examination (temperature, blood pressure and pulse) – to be completed 15 min before any ocular assessment; also to be completed at least  $30 \pm 10$  min before IMP administration
- Slit-lamp examination
  - ✓ Anterior chamber cell
  - ✓ Anterior chamber flare
  - ✓ Chemosis
  - ✓ Bulbar conjunctival injection
  - ✓ Ciliary injection
  - ✓ Corneal edema
  - ✓ Keratic precipitates
- IOP
- BCVA measured by Snellen chart
- Indirect ophthalmoscopy
- Prior medications
- Randomization of the patient
- Dispensation of IMP and administration of the first dose

After IMP administration:

- Distribution of patient diary:
  - Throughout the study, patients or caregivers should record on it: doses and schedule of IMP administration, eye pain VAS scores and cataract surgery-associated symptoms.
- Concomitant medications
- AE assessment (**NOTE:** Expected changes or the presence of inflammation or pain resulting from routine cataract surgery will not be captured as AEs. Additionally, the routine cataract surgery at Day –1 will not be reported as an AE.)

**4.3.2.3 Visit 2 (Day 3 + 1 day)**

At Visit 2, the following activities and assessments will be performed (**NOTE:** All ocular assessments must be performed in both eyes):

- Eye pain (VAS) – to be assessed prior to any physical evaluation

- Eye discomfort – to be assessed prior to any physical evaluation
- Photophobia (VAS) – to be assessed prior to any physical evaluation
- Vital signs examination (temperature, blood pressure and pulse) – to be completed 15 min before any ocular assessment
- Slit-lamp examination
  - ✓ Anterior chamber cell
  - ✓ Anterior chamber flare
  - ✓ Chemosis
  - ✓ Bulbar conjunctival injection
  - ✓ Ciliary injection
  - ✓ Corneal edema
  - ✓ Keratic precipitates
- IOP
- Review of patient diary
- AE assessment (**NOTE:** Expected changes or the presence of inflammation or pain resulting from routine cataract surgery will not be captured as AEs)
- Concomitant medications

#### 4.3.2.4 Visit 3 (Day 8 ± 1 day)

At Visit 3, the following activities and assessments will be performed (**NOTE:** All ocular assessments must be performed in both eyes):

- Eye pain (VAS) – to be assessed prior to any physical evaluation
- Eye discomfort – to be assessed prior to any physical evaluation
- Photophobia (VAS) – to be assessed prior to any physical evaluation
- Vital signs examination (temperature, blood pressure and pulse) – to be completed 15 min before any ocular assessment
- Slit-lamp examination
  - ✓ Anterior chamber cell
  - ✓ Anterior chamber flare
  - ✓ Chemosis
  - ✓ Bulbar conjunctival injection
  - ✓ Ciliary injection
  - ✓ Corneal edema
  - ✓ Keratic precipitates
- IOP
- BCVA measured by Snellen chart
- Review of patient diary

- AE assessment (**NOTE:** Expected changes or the presence of inflammation or pain resulting from routine cataract surgery will not be captured as AEs)
- Concomitant medications

#### 4.3.2.5 Visit 4 (Day 15 ± 2 days)

At Visit 4, the following activities and assessments will be performed (**NOTE:** All ocular assessments must be performed in both eyes):

- Eye pain (VAS) – to be assessed prior to any physical evaluation
- Eye discomfort – to be assessed prior to any physical evaluation
- Photophobia (VAS) – to be assessed prior to any physical evaluation
- Vital signs examination (temperature, blood pressure and pulse) – to be completed 15 min before any ocular assessment
- Slit-lamp examination
  - ✓ Anterior chamber cell
  - ✓ Anterior chamber flare
  - ✓ Chemosis
  - ✓ Bulbar conjunctival injection
  - ✓ Ciliary injection
  - ✓ Corneal edema
  - ✓ Keratic precipitates
- IOP
- BCVA measured by Snellen chart
- Indirect ophthalmoscopy
- Review and return of the patient diary
- Return of the remaining study medication
- AE assessment (**NOTE:** Expected changes or the presence of inflammation or pain resulting from routine cataract surgery will not be captured as AEs)
- Concomitant medications

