## 4. OVERALL DESIGN AND PLAN OF THE STUDY

### 4.1 Overview

This is a phase 3, randomized, parallel-group, double-masked, placebo-controlled, multicenter study.

This study will compare the efficacy and safety of clobetasol propionate ophthalmic nanoemulsion 0.05% to placebo (vehicle), when administering one drop QID during 14 days after routine unilateral cataract surgery.

Approximately a 15% of screening failures is expected. Overall, 210 patients are planned to be randomized into the study. They will be screened across 20 centers in the US. Patients who experience postoperative inflammation on the first day following routine cataract surgery and who meet all other eligibility criteria will be randomized to one of two study groups in a 2:1 ratio to receive either clobetasol propionate ophthalmic nanoemulsion 0.05% (N=140) or placebo (N=70) for the treatment of inflammation and pain associated with cataract surgery.

Patients will undergo routine cataract surgery according to the investigator's normal procedures.

The day of the cataract surgery will be considered Day -1 of the study, whereas the day of the randomization and the first administration of the IMP will be considered Day 1 of the study.

Six study visits are planned: Visit -1 (Screening; Day  $-7 \pm 3$  days), Visit 1 (Baseline; Day 1, 24h after the surgery), Visit 2 (Day 3 + 1 day), Visit 3 (Day 8  $\pm 1$  day), Visit 4 (Day 15  $\pm 2$  days), and Visit 5 (Day 29  $\pm 2$  days) (Table 1). An attempt should be made to schedule patients at approximately the same time during the day at each study visit.

If a patient wants to discontinue from the study, he/she will be treated according to the clinical practice. Patients who discontinue the study treatment will be requested to continue attending their remaining study visits. If the patient does not accept and wants to discontinue from the study, they will be encouraged to at least attend the Early Termination Visit (Section 4.3.2.8) as soon as possible.

An informed consent form (ICF) must be obtained from each patient prior to the commencement of any study procedure. All patients must be given ample time to review the ICF and to ask any question related to the study prior to their participation. All participant patients will be provided with a copy of the signed ICF.

[figure not shown]

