#### 4.3.2.8 Early Termination Visit

At any time, the investigator will make every attempt to ensure that an Early Termination Visit will be held in the case of a patient discontinuing the study (see Section 5.3).

At the Early Termination Visit, the following activities and assessments will be performed (**NOTE:** All ocular assessments must be performed in both eyes):

- Eye pain (VAS) – to be assessed prior to any physical evaluation
- Eye discomfort – to be assessed prior to any physical evaluation
- Photophobia (VAS) – to be assessed prior to any physical evaluation
- Vital signs examination (temperature, blood pressure and pulse) – to be completed 15 min before any ocular assessment
- Physical and eye examination
- Slit-lamp examination
  - ✓ Anterior chamber cell
  - ✓ Anterior chamber flare
  - ✓ Chemosis
  - ✓ Bulbar conjunctival injection

- ✓ Ciliary injection
- ✓ Corneal edema
- ✓ Keratic precipitates
- IOP
- BCVA measured by Snellen chart
- Indirect ophthalmoscopy
- Review and return of the patient diary
- Return of the remaining study medication
- AE assessment (**NOTE:** Expected changes or the presence of inflammation or pain resulting from routine cataract surgery will not be captured as AEs)
- Concomitant medications

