### 6.2 Administration

Study medication will be supplied in single-dose vials containing 0.20 mL (approximately 0.17 mL deliverable volume) per vial. A medication kit contains 6 pouches with 2 strips of 5 vials in each pouch, for a total of 60 vials and a plastic bag labelled with the kit number.

The first dose of the IMP should be administered by the investigator or a designated study team member at Visit 1. After that, the investigator or a designated study team member will remove 4 vials from the opened pouch. He or she will place the removed vials (used one and unused ones) in a bag provided with the kit and store them at the study site in a secure location for traceability. The remaining 5 vials will be returned to the medication kit, for dispensation to the patient. Finally, the patient will receive a kit with 55 vials for their self-administration in the study eye QID for 14 consecutive days.

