### 6.5 Drug Accountability

The Sponsor has the responsibility of providing the IMP for free and perfectly identified and prepared in agreement with GMP's procedure.

The medication of the clinical trial only can be sent to the investigation center after having obtained all the applicable approvals (e.g. IRBs).

The IMP supplier [REDACTED] will send the samples of medication to the Pharmacy Service of the study center together with the pertinent documentation (fundamentally, the analytical memory of the samples).

The Pharmacy Service is responsible of receiving the samples of medication, to verify and/or to assure that they follow the in-force legislation of labelling, to preserve them correctly and to send them to the study center after verifying that all the approvals have been obtained and the contracts have been signed.

The investigator, or the responsible investigator with delegated function, must assure the correct reception in the study center of the medication for the clinical trial (inventory of samples and review of the labelling) as well as his correct storage according to the specific procedure of conservation. The reception and storage of the medication in the study center will be documented properly according the guidelines established in the corresponding SOP.

The IMPs must be tracked using two logs:

- A center-specific log to track the complete inventory (that is, what is shipped between the center and the Sponsor)
- A patient-specific log to track what is dispensed to and returned by the patient. The investigator and the pharmacist, if applicable, must agree not to dispense any IMP to any person, except patients enrolled in the study. The investigator or the pharmacist (if applicable) must maintain an adequate record of the receipt and distribution of the IMPs. This log must be available for inspection at any time.

Patients will be instructed to return all single-dose vials, both used and unused, to the center at Visit 4 or at Early Termination Visit (if applicable), for which compliance will be assessed by the investigator or designee, utilizing the patient diary.

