14.2.16.1	Change from baseline to Day 3, Day 8, Day 15 and Day 29 compared to placebo in the proportion of patients with different discomfort grades. Improvement or no Improvement	FAS	
14.2.16.2	Change from baseline to Day 3, Day 8, Day 15 and Day 29 compared to placebo in the proportion of patients with different discomfort grades. Descriptpve table	FAS	
14.2.17.1	Proportion of patients with no discomfort ("None") compared to placebo at Day 3, Day 8, Day 15 and Day 29.	FAS	
14.2.17.2	Eye discomfort by visit and treatment. Descriptive statistics	FAS	
14.2.18	MMRM. Change over time in the VAS pain score reported in the patients' diaries compared to placebo.	FAS	X
14.2.19	Percentage of patients with anterior chamber cell grade of "0" compared to placebo at Day 8. Sensitivity Analysis	FAS	

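### Visit 4 may fall on Day 13 or 14, before the 14-day course is complete, yet all vials and the diary must be handed back at that visit

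*Protocol*

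**What the plan says.** **Regimen.** Day 1 is the day of the first dose (Protocol 4.1). Under Protocol 6.2 one dose is given at the site and then "the patient will receive a kit with 55 vials for their self-administration in the study eye QID for 14 consecutive days". SAP 6.3.8 fixes the planned number of doses at 56.

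**Collection.** Visit 4 is Day 15 ± 2 days, so Day 13 to Day 17. Protocol 4.3.2.5 lists "Return of the remaining study medication" together with review and return of the diary. Table 1 marks "Return of remaining IMP" and diary return at Visit 4 and at early termination only. Protocol 6.5 adds: "Patients will be instructed to return all single-dose vials, both used and unused, to the center at Visit 4 or at Early Termination Visit". Visit 5 lists neither vial nor diary return.

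**Diary.** It holds "doses and schedule of IMP administration, eye pain VAS scores and cataract surgery-associated symptoms" (Protocol 4.3.2.2). The pain scores feed SAP table 14.2.18, whose title begins "MMRM. Change over time in the VAS pain score reported in the".

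**Patients who stop drug but stay.** Protocol 4.1 says "Patients who discontinue the study treatment will be requested to continue attending their remaining study visits". Protocol 4.3.2.8 provides that "an Early Termination Visit will be held in the case of a patient discontinuing the study", so that visit is tied to leaving the study. Visits 2 and 3 and the unscheduled visit list no vial return.

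**The concern.** A 14-day course that starts on Day 1 runs through Day 14, but the window lets the collection visit fall on Day 13 or 14. No sentence requires Visit 4 to follow the last dose, and none lets a patient seen early keep the remaining vials or the diary. Protocol 4.1 also rules out waivers except for immediate safety concerns and makes adherence to Table 1 mandatory. A site that carries out Visit 4 as listed on Day 13 or 14 therefore takes away the means to finish the course.

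Three things are at stake:

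- delivery of the stated regimen;
- the compliance figure, because doses that were collected count as missed against a fixed 56;
- the last diary pain scores.

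A smaller accountability gap sits beside this. A patient who stops the drug but stays in the study has no scheduled vial return before Visit 4.

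**Working it through.** **The plan's own figure.** 14 days × 4 = 56 doses. The kit has 60 vials and the site removes 5 (1 used, 4 unused), so 55 go home. 55 + 1 site dose = 56. The plan's figure is reproduced.

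**Doses due before a same-clock-time visit.** Protocol 4.1 asks sites to attempt the same time of day at each visit, and Protocol 6.2.2 gives an interval of about 6 hours. For a visit on Day v, doses due = 4 × (v − 1), capped at 56.

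| Visit 4 on | Due before visit | Share of 56 | Lost |
|---|---|---|---|
| Day 13 | 4 × 12 = 48 | 85.7% | 8 |
| Day 14 | 4 × 13 = 52 | 92.9% | 4 |
| Day 15 | 4 × 14 = 56 | 100% | 0 |
| Days 16 and 17 | 56 (cap) | 100% | 0 |

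**Other dose and visit times.** Doses taken = d + 4 × (v − 2) + k, capped at 56. Here d is the number of doses on Day 1 and k the number taken on the visit day before the visit. I assume d from 2 to 4 and k from 0 to 4.

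- Day 13, fewest: 2 + 44 + 0 = 46, lost 10. Most: 4 + 44 + 4 = 52, lost 4.
- Day 14, fewest: 2 + 48 + 0 = 50, lost 6. Most: 4 + 48 + 4 = 56, lost 0.
- Day 15, fewest: 2 + 52 + 0 = 54, lost 2. Most: 56, lost 0.

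**Compliance against 56.** SAP section 5 sets the limit at 80%: 0.80 × 56 = 44.8, so 45 doses are needed.

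- Full course: 56 − 45 = 11 missed doses tolerated.
- Same-time Day 14 visit: 52 − 45 = 7.
- Same-time Day 13 visit: 48 − 45 = 3.

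A Day 13 patient who misses 4 of the 48 available doses took 44/48 = 91.7% of them but scores 44/56 = 78.6%. A same-time early patient who misses nothing scores 85.7% or 92.9% and cannot enter the SAP's 100% category. The early visit alone does not take anyone below 80%: the lowest case is 46/56 = 82.1%. The SAP's second measure, based on exposure dates, does not charge the collected doses: (13 − 1) × 4 = 48 planned.

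**Diary.** Assuming one pain score a day (the protocol gives no frequency), 12/14 = 85.7% or 13/14 = 92.9% of days are kept.

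**Patients affected.** The documents give no distribution of visit days. For scale only, each 10% of patients seen on Day 13 or 14 is 0.10 × 210 = 21 patients.

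**Vials held after stopping drug.** A Day 3 stop, with 6 to 8 doses taken (5 to 7 of them from home vials), leaves 48 to 50 of 55 vials for 10 to 14 days until Visit 4. A Day 8 stop, with 26 to 28 doses taken, leaves 28 to 30 vials for 5 to 9 days.

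**The case against.** The strongest reply is that no sentence says dosing stops at an early Visit 4. The protocol asks for 14 consecutive days in several places, so a site could book the visit on Day 15 or let the patient finish. This stands in part: an early visit sets two instructions against each other, and a shortened course is one way of resolving them. But 6.5 asks for all vials at Visit 4 and 4.1 makes Table 1 binding, so the site that performs the visit as written is the one that cuts the course. A site that leaves the vials with the patient departs from 6.5.

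It is also fair that 8 and 4 hold only for same-time visits. A later visit hour on Day 14 could cost nothing.

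Several stronger readings are tempting and are not supported:

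- *That the main results are at risk.* Both main endpoints are at Day 8, and their per-protocol set uses compliance at Visit 3.
- *That Visit 4 assessments are compromised by the collection.* Vials are handed back at that visit, not before it.
- *That a known, sizeable share of patients loses doses.* Any count, such as 21 to 84 patients at 10% to 40%, rests wholly on an assumed share. The 40% figure treats the nominal Day 15 as no likelier than the edges of the window.
- *That leftover vials bias efficacy.* Nothing forbids earlier return, Protocol 6.5 keeps a patient-specific log, and 6.6 has diaries reviewed at each visit during treatment. This part is mostly site practice.

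**Conclusion.** The point holds and is minor. An in-window Visit 4 on Day 13 or 14, carried out as written, ends the course about 8 or 4 doses short at a same-time visit (roughly 4 to 10 and 0 to 6 across plausible dose and visit times). It also ends the diary one or two days early.

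Three consequences remain. The stated regimen is not fully delivered to these patients. On the fixed-56 measure, a same-time early patient cannot reach 100%, and the margin above 80% shrinks from 11 missed doses to 3 (Day 13) or 7 (Day 14). The diary pain analysis loses its last points; SAP 6.3.6.2 treats it as exploratory, although SAP 8.1 marks it for the top-line outputs.

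The 80% margin could affect per-protocol membership only for analyses after Visit 3. SAP section 5 does not say which compliance measure applies there, and SAP 8.1 lists the other secondary tables on the full analysis set only.

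The conflict in the text is certain. The dose counts rest on 6-hourly dosing from Visit 1 and on visit times, and the number of patients affected cannot be estimated from the documents.

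**What to change.** Keep the ± 2 day window. In Table 1, 4.3.2.5 and 6.5, state that a patient seen at Visit 4 before the last planned dose keeps the remaining vials and the diary, completes the course, and returns both promptly afterwards, by courier or at Visit 5 at the latest. Amend 4.3.2.6 and the Visit 5 column of Table 1 to allow that return. The rule also covers a Day 15 patient with one or two doses left. The SAP needs no change, because 56 doses can then be reached.

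The cost is amendment wording, with no added patients or visits. Drug reconciliation is later for these patients: in the worst case, Day 13 to a Visit 5 on Day 31, 18 days. That is why prompt return should be the default and Visit 5 the backstop.

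A one-sided window of Day 15 + 2 days, as Visit 2 already has, is optional and a trade-off. It shortens the window from 5 days to 3 and gives up on-treatment Visit 4 readings on Days 13 and 14. With the last dose at 55 × 6 = 330 hours, same-time visits on Days 15 to 17 (336 to 384 hours) would fall 6 to 54 hours after it. The synopsis and 4.1 would also need editing.

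As a small accountability clarification, Table 1 and 6.5 could ask for vial return at the first visit at or after permanent discontinuation of study drug.
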